### **20.3 Secondary Efficacy Endpoints**

All of the instruments used to measure SSIB or depression constitute serial continuous and ordinal outcomes that will be analyzed using MMRM with LOCF, which accounts for missing data and early discontinuations. Results will be presented separately for each treatment group.

The models will include treatment group, study visit, the interaction between study visit and treatment group, the randomization baseline of the variable being analyzed, and the four baseline stratification factors as fixed effects. The reason for missing data will be evaluated as a condition of MMRM analysis.

### **20.4 Other Efficacy Endpoints**

The following additional endpoints will be recorded and analyzed by treatment group for both study phases:

- Dose per treatment group
- Suicide rates
- Proportion of participants who are treated with new SSRIs or have increased SSRI dosages
- Proportion of participants who discontinue SSRIs or have reduced SSRI dosages
- Efficacy for each BPRS factor.

Dose per treatment group will be displayed graphically over time per study treatment group. The percent decreasing and increasing over time relative to starting dose will be displayed per study treatment group.

Time to all-cause study dropout will be displayed using a Kaplan-Meier lifetable.

The following three measures will be separately evaluated using a two-sided Fisher Exact test to compare treatments:

- the need to implement a new treatment plan.
- an increase in suicidal ideation (a score of  $\geq 4$  on the C-SSRS, emergent suicidality requiring hospitalization).
- an increase in depressive symptoms (a score increase of  $\geq 5$  from the previous on-study visit for two consecutive visits on the MADRS total score).

The number of hospitalization and ER visits per subject will be evaluated using a Wilcoxon Rank Sum test to compare each study treatment group.

The proportions of participants discontinuing SSRIs or reducing SSRI dosages will be displayed graphically over time per study treatment group. The percent discontinuing SSRIs and reducing SSRI dosages relative to starting dose will be displayed per study treatment group.

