6.6 Dose Selection

Lurasidone is an FDA-approved medication for depressive episodes associated with Bipolar I Disorder (bipolar depression) as monotherapy and as adjunctive therapy with lithium or valproate at doses of 20 mg to 120 mg daily. The target dose of 66 mg/day is based on the mean daily dose

of lurasidone observed during the fixed titration phase of the lurasidone registration trial for its indication in bipolar depression (Loebel et al., 2014b) and further validated in the STABIL-B trial (Javitt, et. al. 2018). Up-titrations are permitted if needed to doses of 99 or 132 mg/day, and down-titrations are permitted to 33 or 49.5 mg/day, which span the range of doses used in clinical studies of lurasidone (Loebel et al., 2014a; Loebel et al., 2014b).

DCS is well tolerated as a second-line treatment for TB at therapeutic split daily oral doses in the range of 500 to 1000 mg/day. Based on prior clinical results and animal studies, it is anticipated that therapeutic effects of DCS will be associated with plasma doses in excess of 25 μ g/mL, which in turn are generally associated with daily oral doses in excess of 10 mg/kg (i.e., 700 mg/day for a 70 kg) individual. A starting daily dose at 700 mg DCS and 33 mg lurasidone will be used, and then titrated over 2 days to the target dose of 950 mg DCS and 66 mg lurasidone. Down-titrations of DCS to 825 or 700 mg/day are available in the case of side effects to permit reduced dosing within the anticipated therapeutic range (700 – 950 mg/day). The maximum dose of 950 mg/day is within FDA-approved dosing limits for DCS.

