10.3 Investigational Product Titration

Investigators will have the ability to increase the lurasidone dose at any point after the initial titration period for control of agitation or psychotic symptoms, or to decrease both the DCS and lurasidone dose in response to somnolence. No other dose modifications will be allowed.

Titrations of investigational product will be affected while maintaining a blinded study design (see Table 2 for NRX-101 and Table 3 for lurasidone). Up-titration will increase the lurasidone dose, and will not alter the DCS dose. Down-titration decreases the total daily dose of both lurasidone and DCS in the NRX-101 group and only the lurasidone dose in the lurasidone group.

Table 2 NRX-101 Dose Titration

	Morning Dose (mg)		Evening Dose (mg)		Total Daily Dose (mg)	
Day	DCS	Lurasidone	DCS	Lurasidone	DCS	Lurasidone
1	350	16.5	350	16.5	700	33
2	475	33	475	33	950	66
3	475	33	475	33	950	66
4	475	33	475	33	950	66
5	475	33	475	33	950	66
Maintenance Dose	475	33	475	33	950	66
Up-titration (if needed)						
step 1	475	33	475	66	950	99
step 2	475	66	475	66	950	132
Down-titration (if needed)						
step 1	350	16.5	475	33	825	49.5
step 2	350	16.5	350	16.5	700	33

Table 3 Lurasidone Dose Titration

	Morning	Morning Dose (mg)		Evening Dose (mg)		y Dose (mg)
Day	DCS	Lurasidone	DCS	Lurasidone	DCS	Lurasidone
1	0 (placebo)	16.5	0 (placebo)	16.5	0 (placebo)	33
2	0 (placebo)	33	0 (placebo)	33	0 (placebo)	66
3	0 (placebo)	33	0 (placebo)	33	0 (placebo)	66
4	0 (placebo)	33	0 (placebo)	33	0 (placebo)	66
5	0 (placebo)	33	0 (placebo)	33	0 (placebo)	66
Maintenance Dose	0 (placebo)	33	0 (placebo)	33	0 (placebo)	66
Up-titration (if needed)						
step 1	0 (placebo)	33	0 (placebo)	66	0 (placebo)	99
step 2	0 (placebo)	66	0 (placebo)	66	0 (placebo)	132
Down-titration (if needed)						
step 1	0 (placebo)	16.5	0 (placebo)	33	0 (placebo)	49.5
step 2	0 (placebo)	16.5	0 (placebo)	16.5	0 (placebo)	33

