Dosage, Route of Administration, and Schedule:	
On Day 1, eligible participants will be randomized to blinded NRX-101 or lurasidone and placebo capsules administered twice daily (BID).
 
Investigational product will be titrated over 2 days. In the case of randomization to NRX-101, the blinded investigational product will consist of daily doses of 700 mg DCS and 33 mg lurasidone and increasing the dose to 950 mg DCS and 66 mg lurasidone on second day. The total daily NRX-101 maintenance dose for Day 3 through Day 42 is 950 mg DCS and 66 mg lurasidone. In the event a patient experiences agitation or psychosis, a blinded up-titration is permitted. Similarly, a blinded step-down titration is allowed for somnolence. In order to maintain the blind, lurasidone/placebo capsules will be administered to ensure participants take the same number of capsules with each dose administration.
 
NRX-101 is supplied in capsules that contain 237.5 mg or 175 mg of DCS and a second capsule that contains 8.25 mg, 16.5 mg, or 33 mg of lurasidone. In order to maintain the blind, lurasidone/placebo capsules will be administered to ensure participants take the same number of capsules with each dose administration.
 
In the case of randomization to lurasidone, the blinded investigational product will start with doses of 33 mg lurasidone and increasing the dose to 66 mg. The total daily lurasidone maintenance dose for Day 3 through Day 42 is 66 mg.

Endpoint Adjudication	
All rating sessions for MADRS-10 and C-SSRS will be recorded as audio files and reviewed by central master-raters with >25 years' experience. Any MADRS-10 total score that differs by more than three points from the master-rater score will be deemed non-congruent. All non-congruent subject-visits from any site with >10% non-congruent scores will be sent to an independent adjudicator previously determined to have >90% concordance with study master raters on standardized training data. In the event of adjudication as above, the independent outside rater score shall be considered as the subject-visit primary study endpoint.

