## 6.5 Dose Selection

Lurasidone is an FDA-approved medication for depressive episodes associated with Bipolar I Disorder (bipolar depression) as monotherapy and as adjunctive therapy with lithium or valproate at doses of 20 mg to 120 mg daily. The target dose of 66 mg/day is based on the mean daily dose of lurasidone observed during the fixed titration phase of the lurasidone registration trial for its indication in bipolar depression ([Loebel et al., 2014b](#)) and further validated in the STABIL-B trial ([Javitt, et. al. 2018](#)). Up-titration are permitted if needed to doses of 99 or 132 mg/day, and down-titration are permitted to 33 or 49.5 mg/day, which span the range of doses used in clinical studies of lurasidone ([Loebel et al., 2014a](#); [Loebel et al., 2014b](#)).

DCS is well tolerated as a second-line treatment for TB at therapeutic split daily oral doses in the range of 500 to 1000 mg/day. Based on prior clinical results and animal studies, it is anticipated that therapeutic effects of DCS will be associated with plasma doses in excess of 25 µg/mL, which in turn are generally associated with daily oral doses in excess of 10 mg/kg (i.e., 700 mg/day for a 70 kg) individual. A starting daily dose at 700 mg DCS and 33 mg lurasidone will be used, and then titrated over 2 days to the target dose of 950 mg DCS and 66 mg lurasidone. Down-titration of DCS to 825 or 700 mg/day are available in the case of side effects to permit reduced dosing within the anticipated therapeutic range (700 – 950 mg/day). The maximum dose of 950 mg/day is within FDA-approved dosing limits for DCS.

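### Dose changes are to be shown relative to the starting dose, which is also the lowest permitted dose, so no down-titration can be counted as a decrease

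*SAP*

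**What the plan says.** SAP 20.4 lists dose per treatment group among the other efficacy endpoints and plans two displays: a graph of dose over time by group, and a summary of direction in which the "percent decreasing and increasing over time relative to starting dose will be displayed per study treatment group". Protocol 16.8.8 has the same sentence. Neither section defines the reference dose.

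Elsewhere the term has one use. SAP 6.5 says "A starting daily dose at 700 mg DCS and 33 mg lurasidone will be used", and Protocol 6.6 says the same. For the comparator arm, the SAP synopsis says that blinded product "will start with doses of 33 mg lurasidone and increasing the dose to 66 mg". The later dose has its own name: for NRX-101 the "maintenance dose for Day 3 through Day 42 is 950 mg DCS and 66 mg lurasidone", and for the comparator "The total daily lurasidone maintenance dose for Day 3 through Day 42 is 66 mg".

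On reductions, Protocol 6.6 says "down-titrations are permitted to 33 or 49.5 mg/day" for lurasidone and "Down-titrations of DCS to 825 or 700 mg/day are available in the case of side effects". Protocol 10.3 says "Down-titration decreases the total daily dose of both lurasidone and DCS in the NRX-101 group" and only the lurasidone dose in the comparator arm. It adds that up-titration leaves DCS unchanged and that no other dose modification is allowed. The levels are set out in Protocol Tables 2 and 3.

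**The concern.** A display of increases and decreases is informative only if the reference is a dose that participants can move above and below. Here the reference is given on Day 1 only, everyone is scheduled to leave it on Day 2, and it coincides with the bottom of the permitted range. A programmer following the text would label a participant stepped down to 49.5 mg lurasidone as increased. That is the wrong sign, not merely a loss of detail.

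Direction matters because Protocol 10.3 ties up-titration to agitation or psychotic symptoms and down-titration to somnolence, so the shares titrated each way carry tolerability information. Lurasidone is also both the comparator and a component of NRX-101, with permitted daily doses from 33 to 132 mg in either arm. A between-arm difference in titration is useful context for the MADRS comparison and for the akathisia objective measured by BARS.

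**Working it through.** **Step 1: reproduce the daily totals.** Inputs are the morning and evening doses in Protocol Table 2. Table 3 has the same lurasidone doses with placebo for DCS. Daily total = morning + evening, in mg.

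| Level | DCS | Lurasidone |
|---|---|---|
| Day 1 | 350 + 350 = 700 | 16.5 + 16.5 = 33 |
| Day 2 and maintenance | 475 + 475 = 950 | 33 + 33 = 66 |
| Up step 1 | 475 + 475 = 950 | 33 + 66 = 99 |
| Up step 2 | 475 + 475 = 950 | 66 + 66 = 132 |
| Down step 1 | 350 + 475 = 825 | 16.5 + 33 = 49.5 |
| Down step 2 | 350 + 350 = 700 | 16.5 + 16.5 = 33 |

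These match the printed totals. Day 1 and down step 2 are identical.

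**Step 2: classify each level against the two candidate references.**

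| Level | Against Day 1 (700/33) | Against maintenance (950/66) |
|---|---|---|
| Maintenance | increased | at reference |
| Up steps 1 and 2 | increased | lurasidone above, DCS at reference |
| Down step 1 | increased | both below |
| Down step 2 | unchanged | both below |

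Against Day 1 no level is a decrease. DCS also reads as increased for an up-titrated participant, although up-titration does not change it.

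**Step 3: size.** The documents give no titration rates, so the shares here are assumptions. Let u, d1 and d2 be the shares of an arm up-titrated, at down step 1 and at down step 2, with everyone still dosed. For lurasidone:

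- Against Day 1: increased = 1 − d2; unchanged = d2; decreased = 0.
- Against maintenance: above = u; at = 1 − u − d1 − d2; below = d1 + d2.

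| u = d1 = d2 | Against Day 1: increased / unchanged / decreased | Against maintenance: above / at / below |
|---|---|---|
| 0% | 100 / 0 / 0% | 0 / 100 / 0% |
| 5% | 95 / 5 / 0% | 5 / 85 / 10% |
| 10% | 90 / 10 / 0% | 10 / 70 / 20% |
| 20% | 80 / 20 / 0% | 20 / 40 / 40% |

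**Step 4: a difference between arms.** Suppose 10 of 37 on NRX-101 and 2 of 37 on lurasidone are at down step 1, and the rest at maintenance. Against maintenance, 10/37 = 27% and 2/37 = 5% are below. Against Day 1, both arms show 0% decreased and 100% increased.

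**Step 5: what a graph of mean dose would add.** In the same example, mean lurasidone is (10 × 49.5 + 27 × 66)/37 = 61.5 mg against (2 × 49.5 + 35 × 66)/37 = 65.1 mg, so a difference would be visible. Opposite titrations can cancel, however. Up step 1 adds 99 − 66 = 33 mg and down step 1 removes 66 − 49.5 = 16.5 mg. With 5 participants up and 10 down, the net change is 5 × 33 − 10 × 16.5 = 0. The mean stays at 66 mg although 15 of 37 were titrated.

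**The case against.** The strongest reply is that the effect is small. This is one untested descriptive sentence, the underlying dose data are unaffected, and the table can be corrected at any time. All of that stands.

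Four stronger conclusions might be inferred, and the documents do not support them.

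- *That titration would otherwise go unreported.* The sentence just before the one at issue plans a graph of dose over time by group, which does not depend on the reference dose and may show average drift. For each adverse event, SAP 12.2.1 also records whether product was up- or down-titrated. What remains is narrower: if the graph plots means, it does not give the share titrated each way (step 5), and no table of the adverse-event action field by arm is specified.
- *That nearly 100% read as increased whatever the titration rate.* Step 2 participants read as unchanged, so the percent increased falls as step 2 use rises, from 100% to 80% over the assumed range.
- *That 0% decreased is unconditional.* SAP 12.2.1 recognises temporary and permanent discontinuation, and SAP 20.4 does not say how these count. Scored as zero dose, they would appear as decreases, but they would not be titrations.
- *That the efficacy comparison is compromised.* Nothing in the primary model, the testing hierarchy or the sample size uses this display.

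It can also be said that the authors meant the maintenance dose. That reading would make the display work, but neither section says so, and both documents use the term for Day 1 and name maintenance separately.

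**Conclusion.** The rule is wrong as written. Under the documents' own use of the term, no permitted titration in either arm can register as a decrease. A reduction to step 1 registers as an increase, a reduction to step 2 as no change, and ordinary maintenance cannot be told apart from up-titration. The percent decreased is 0% in both arms, provided interruptions are not scored as zero dose. Everyone dosed after Day 1 counts as increased except participants at step 2.

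This rests on Day 1 being the starting dose and on the levels in Protocol Tables 2 and 3 being the only ones used. The percentages in the working depend on assumed titration shares; the classification does not. The consequence is confined to a descriptive display whose summary of direction would mislead.

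**What to change.** In SAP 20.4 and Protocol 16.8.8, change the reference in the study-drug sentence to *the scheduled maintenance dose in Protocol Tables 2 and 3, from Day 3 onward*. Name the Protocol explicitly, because Table 2 in the SAP is the sample-size table. Report by arm the percent above, at and below that dose, for lurasidone in both arms and for DCS in the NRX-101 arm, since up-titration moves only lurasidone. State how interruptions and discontinuations are counted.

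Leave the SSRI sentence in the same sections alone. There the starting dose is the participant's own SSRI dose, and the problem does not arise. No dosing rule changes.

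The cost is one sentence in each document and one reprogrammed table. The data should come from dispensed-kit and dose-change records: Protocol 11.1 dispenses Kits 2 to 5 only when a titration is required and puts a kit number on the label, and 11.1.2 requires dispensation logs. The documents do not say that a complete dose history is held in the eCRF, so confirm that before programming.

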8.1 Inclusion Criteria

- 1. 18 to 65 years of age, inclusive, at Screening.
- 2. Able to understand and provide written and dated informed consent prior to screening.
- 3. Deemed likely to comply with the study protocol, including communication of adverse events (AEs) and other clinically important information, including adherence to the text messaging component of the trial.
- 4. Will follow medical directions for psychiatric care, as appropriate, per the standard of care.
- 5. Resides in a stable living situation. A stable living situation will be defined as a minimum of 3 months at the same address with a reasonable expectation that the situation will continue such that the patient's ability to participate in the study will not be affected. Please note that housing in a shelter of any kind will not be deemed stable housing.
- 6. Previously diagnosed and treated for Bipolar Disorder (BD) I or II according to the criteria defined in the DSM-V.
- 7. Has an identified reliable informant/care partner, that is willing to provide information and/or supportive care as necessary.
- 8. The diagnosis of BD will have been made by a psychiatrist or other qualified licensed psychiatric provider able to render a diagnosis and be supported by the MINI 7.0.2.
- 9. Treatment with a medication indicated for use in bipolar disorder in the past five years (See Appendix 4 for list).
- 10. Confirmed active suicidal ideation (without the intention to act) as evidenced by an answer of 'Yes' on item 3 and/or 4 and not requiring hospitalization at Screening and an answer of 'No' on item 5 of the C-SSRS within 4-weeks of Screening.
- 11. A total score greater than or equal to 30 on the 10 items of the MADRS.
- 12. No co-morbidities, as ascertained by medical history, physical examination (including measurement of vital signs), clinical laboratory evaluations, and electrocardiogram (ECG) which might interfere with compliance or the ability to assess efficacy or safety.
- 13. If female, a status of non-childbearing potential or use of an acceptable form of birth control per the following criteria, and agrees to continue use of the same method of birth control for the duration of study participation:

- a. Non-childbearing potential: physiologically incapable of becoming pregnant (i.e. permanently sterilized [status post-hysterectomy, bilateral tubal ligation] or post-menopausal with last menses at least one year prior to screening); or

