9.1.2 Treatment and Follow-up Periods

Participants that continue to meet MADRS and C-SSRS eligibility will be randomized to receive the first dose of blinded treatment on Day 1. This visit will be followed by Treatment Period visits at Days 7, 14, 28, and 42. Following completion of the Treatment Period, participants will be

contacted via telephone for follow-up on Day 70. In order to allow scheduling flexibility, and (considering pandemic related limitations), visit windows will be allowed as noted in Table 1. Participants will be withdrawn from the study if their urine toxicology screenings at two consecutive study treatment visits are positive for cocaine, opiates, non-prescribed amphetamines, or non-prescribed barbiturates.

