### 16.3 Secondary Hypotheses

The secondary hypothesis are that:

- treatment with NRX-101 is superior to lurasidone in improving symptoms of suicidality as measured by the CGI-SS over 6 weeks of treatment. The null hypothesis is the mean change from baseline of CGI-SS for NRX-101 is greater than or equal to the mean change from baseline of CGI-SS for lurasidone while the alternative hypothesis is that the mean change from baseline of CGI-SS is less than the mean change from baseline of CGI-SS for lurasidone (improvement). Baseline is defined as CGI-SS score at this study entry.
- that NRX-101 is superior to lurasidone in time to treatment failure as defined as: study discontinuation due to Adverse Events; psychiatric hospitalization; or requiring a change in antidepressant treatment. Time to treatment failure may be ascertained as the treating physician's determination of a study discontinuation due to lack of efficacy; withdrawal due to a treatment related adverse event a psychiatric hospitalization; or the patient requiring any change in their baseline antidepressant, mood stabilizer, or antipsychotic medication. Titration or change in timing of administration of study medication will not be considered a failure of therapy. Lack of efficacy is defined as the need to implement a new treatment plan or an increase in suicidal ideation (a score of 4 or 5 on the C-SSRS, emergent suicidality requiring hospitalization), or increase in depressive symptoms (a score increase of  $\geq 5$  for two consecutive visits on the MADRS total score). The need to implement a new

treatment plan includes the addition of new antidepressant medication or somatic treatment (e.g. ECT or rTMS treatment) or an escalation of care such as hospitalization (i.e. moving the patient from outpatient care to initiating inpatient, partial or day hospitalization). Time to failure will be assessed using a Kaplan-Meier lifetable. The formal hypothesis test will be to detect a 0.421 hazard ratio (HR) with 80% power for a two-sided test using a proportional hazard model; a 0.545 hazard ratio reaches two-sided  $p=0.05$ .

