#### 19.4 Estimand Structure

Analyses will be conducted in accordance with ICH E9 (R1) analysis principles as summarized below.

Primary scientific question of interest	The primary study hypothesis is that treatment with NRX-101 is superior to lurasidone in improving symptoms of depression as measured by the MADRS over 6 weeks of treatment. The null hypothesis for the primary endpoint is the mean change from baseline of MADRS-10 for NRX-101 is the same as lurasidone while the alternative hypothesis is that the mean change from baseline of MADRS-10 is larger than the mean change from baseline of MADRS-10 for lurasidone. Baseline is defined as MADRS-10 score at Visit 2 (randomization).
Target population	The mITT population will be the primary analysis population. The mITT population is defined through appropriate inclusion/exclusion criteria as specified in the protocol and blinded BDRM decisions.
Treatment of interest	NRX-101
Outcome Variables	MADRS-10 (and C-SSRS) will be recorded as audio files and reviewed by central master-raters with any non-congruent subject-visits from any site with >10% non-congruent scores sent to a qualified independent adjudicator to be considered as the subject-visit primary study endpoint.
Summary Measure	The contrast-estimated MADRS-10 Week 6 MMRM will use all post-randomization data with LOCF in the mITT population excluding all outcomes after BDRM-approved exclusions. The model will include treatment and the following four baseline covariates in addition to baseline MADRS-10: (1) sex, (2) mood stabilizer use, (3) anti-psychotic use, and (4) evidence of suicide event in their lifetime. The model will include treatment group, study visit, the interaction between study visit and treatment group, baseline MADRS-10, and the four baseline covariates as fixed effects. An unstructured error structure will be assumed.
Intercurrent Events	A BDRM will adjudicate all intercurrent events which may redact outcomes after disqualifying events; these intercurrent events may represent major protocol deviations.

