### 20.2 Other Time to Event Efficacy Endpoints

Other time-to-event outcomes (all-cause discontinuation, and time to remission) further characterize this multi-component disorder. Time to event is a more sensitive measure than an assessment at a fixed time. Time to such events will be displayed using a Kaplan-Meier lifetable,

with the treatment groups compared using two-sided unstratified log rank tests (secondary) and a proportional hazard model (primary) to include the above cited baseline covariates.

Treatment Failure will be centrally judged blind in real time by the study physician using baseline measures of depression and suicidality as a guide. Treatment failure is defined above.

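### SAP 20.4 measures MADRS worsening from the previous visit, so a single rise that is then held is not counted while a partial rebound can be; SAP 16.3 uses the same criterion with no reference visit

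*SAP*

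**What the plan says.** SAP 20.4 lists three measures to be compared between arms by two-sided Fisher exact test. The third is an increase in depressive symptoms, defined as a MADRS rise of at least 5 "from the previous on-study visit for two consecutive visits on the MADRS total score".

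SAP 16.3 uses the same threshold and the same two-visit condition as one branch of lack of efficacy, which feeds time to treatment failure: "or increase in depressive symptoms (a score increase of" at least 5 points "for two consecutive visits on the MADRS total score". No reference visit is named there. The Protocol has the criterion in 16.3.3 and 16.8.8 and names no reference in either place. The previous-visit wording therefore appears only in SAP 20.4, and SAP 13 says that the SAP governs where the two documents differ.

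SAP 20.2 adds that treatment failure is judged centrally and blind, "using baseline measures of depression and suicidality as a guide". For the primary analysis, SAP 19.4 fixes the MADRS baseline at Visit 2, the randomization visit. After baseline, MADRS is taken at the "Treatment Period visits at Days 7, 14, 28, and 42" (Protocol 9.1.2).

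Time to treatment failure is third in the testing hierarchy of SAP 18.3. The stand-alone worsening measure in 20.4 is outside it.

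**The concern.** A count of patients whose depression worsened should pick up those who become clearly worse and stay worse. A rule whose reference moves with each visit tests something else: whether the score is still climbing at the second visit. Once a patient reaches a new, worse plateau, the step to the next visit is near zero and the condition fails, however large the first rise was. The same rule can be met by a patient who improved greatly and gave a little back.

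The second issue is consistency. The criterion appears with the previous visit as reference in 20.4, with no reference in 16.3, and beside a pointer to baseline in 20.2. Two programmers could derive different event lists from the same data, and one of those lists contributes to an endpoint in the hierarchy.

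**Working it through.** **1. The plan's own figure.** No rate is stated for the worsening rule. The nearest stated figure belongs to time to treatment failure, which is designed "to detect a 0.421 hazard ratio (HR) with 80% power for a two-sided test using a proportional hazard model", with 0.545 as the hazard ratio that reaches two-sided p = 0.05. With equal allocation (Schoenfeld):

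- Events = 4 × (1.960 + 0.842)² / (ln 0.421)² = 4 × 7.85 / 0.748 ≈ 42.
- Critical hazard ratio = exp(-2 × 1.96 / √42) = 0.546, against 0.545 stated.

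The two stated ratios agree with each other at 42 events, a count the plan does not give. They depend on the reference visit only through the number of events.

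**2. What 20.4 requires.** Write X(k) for MADRS at visit k. Read literally, the rule is X(k) - X(k-1) ≥ 5 and X(k+1) - X(k) ≥ 5. Adding the two gives X(k+1) - X(k-1) ≥ 10. Days 1, 7, 14, 28 and 42 give four steps and three consecutive pairs of steps. If Day 1 is not an on-study visit, which the SAP does not settle, there are three steps and two pairs.

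**3. Worked series.** The comparison rule is X(k) - X(Day 1) ≥ 5 at two consecutive post-baseline visits. All series start at or above the entry threshold of 30 (Protocol 8.1).

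| MADRS, Days 1/7/14/28/42 | Steps | Counted by 20.4 | Counted against baseline |
|---|---|---|---|
| 34/34/46/46/46 | 0, +12, 0, 0 | No | Yes |
| 34/54/54/54/54 | +20, 0, 0, 0 | No | Yes |
| 34/46/50/50/50 | +12, +4, 0, 0 | No | Yes |
| 34/40/46/46/46 | +6, +6, 0, 0 | Yes, if Day 1 is an on-study visit | Yes |
| 40/15/20/25/25 | -25, +5, +5, 0 | Yes | No |
| 40/20/40/40/40 | -20, +20, 0, 0 | No | No |

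**4. Size, by simulation.** SAP 18.2 supplies the SD of change (13.4) and the mean changes (-10 for lurasidone, -16 for NRX-101). Not in the documents and assumed here: SD of change rising from 8 at the first post-baseline visit to 13.4 at Day 42, correlation 0.7 between adjacent visits, and no dropout.

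| Mean change at Day 42 | Sustained ≥5 above baseline | Counted by 20.4 | Sustained but missed by 20.4 (% of all patients) |
|---|---|---|---|
| -10 | 14% | 9% | 10% |
| -16 | 7% | 5% | 5% |

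At -10, the two rules agree on 14 - 10 = 4% of patients, so 9 - 4 = 5% are counted by 20.4 without sustained worsening over baseline. At -16 they agree on 7 - 5 = 2%, and 5 - 2 = 3% are counted by 20.4 only. If each arm followed its planned course, the missed patients would number about 37 × 0.10 + 37 × 0.05 ≈ 5.6 of 74.

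**5. Sensitivity.** A second set of assumptions used entry mean 35, SD 4, floor 30; SDs of change 7, 9, 11.5 and 13.4; and correlation 0.5 to 0.85.

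- At -10, 20.4 counts 5-9% against 10-13% by the baseline rule.
- At -16, it counts 2-6% against 4-6%.
- Across both courses, 20.4 misses 69-81% of patients with sustained worsening over baseline, and 35-82% of those it counts are not sustained above baseline.

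The net difference in totals is not stable. At -16 with correlation 0.5, 20.4 counts more patients (5.9%) than the baseline rule (3.7%). The mismatch in who is counted persists throughout.

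**The case against.** **The rule may mean something else.** It could be read as a rise of at least 5 from the visit before the rise, held at the next visit. That reading counts every held-rise example above. It would also count far more patients: 17-26% at -10 and 9-17% at -16 under the second set of assumptions. The text does not say this, so the possibility is a further reason to reword it.

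**Relapse is a legitimate kind of worsening.** Counting loss of an earlier gain is defensible, and SAP 9.1 has post-baseline MADRS rated over the period since the last assessment. This stands as a point about purpose. But 20.4 as written does not capture relapse reliably either: 40/20/40/40/40 loses the whole gain and is not counted.

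**Time to treatment failure has other routes.** Medication change, hospitalization, withdrawal for a treatment-related adverse event, a new treatment plan and a C-SSRS score of 4 or 5 can all make a patient an event, and SAP 20.2 does point towards baseline. This stands. A reader might infer that time to treatment failure classifies the wrong patients. The documents do not support that: 16.3 does not contain the previous-visit wording, and an unnamed reference is an ambiguity, not a wrong rule.

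**Two further over-readings.** One might infer that any patient 12 points above baseline at Day 14 who stays there is missed. That holds only when the rise comes in one jump; 34/40/46/46/46 qualifies if Day 1 counts. One might also size the problem on a flat mean course, where about 23% of all patients would be missed, but SAP 18.2 assumes improvement in both arms.

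**Conclusion.** The point holds for SAP 20.4. Followed literally, its stated rule leaves out a large rise that is then held and admits a partial rebound that stays well below baseline. The worked series show this without any distributional assumption. At the SAP's own mean changes, about 10% (at -10) and 5% (at -16) of all patients would be sustained worseners whom the rule misses, roughly 70% or more of that group. Those rates rest on assumed visit SDs, an assumed correlation and no dropout, and should be read as illustrative.

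For time to treatment failure the conclusion is narrower. The criterion has no stated reference in 16.3, only a guide in 20.2, and a different reference in 20.4. The sections can therefore give different event lists. The effect on that endpoint has not been quantified and is limited by its other components. Neither the primary analysis nor its Type I error is affected. The wording should be settled before database lock.

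**What to change.** - **SAP 20.4:** replace the moving reference with one fixed reference that must be exceeded at two consecutive post-baseline visits. An example is MADRS at least 5 above the Visit 2 baseline already used in SAP 19.4.
- **Day 1:** state whether it counts as an on-study visit wherever that term is kept.
- **SAP 16.3, 20.2 and 20.4:** reconcile these so that the criterion has one stated reference and says whether the rise must be held. In 16.3 the criterion defines lack of efficacy leading to discontinuation. The request there is for consistency between the sections; which discontinuation rule applies is for the sponsor and investigators to decide.
- **Relapse:** a baseline reference does not count a patient who improves and then returns to baseline, such as 40/20/40/40/40. If that matters, report relapse from the best post-baseline score as a separate descriptive count.

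The cost is a few sentences in the SAP and a short change to one derived variable. It needs no new data, visits or sample size.
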